LIST OF ABBREVIATIONS

Abbreviation	Explanation
AE	Adverse event
CI	Confidence interval
CRF	Case report form
CRP	C-Reactive Protein
DSMC	Data Safety and Monitoring Committee
EQ-5D	EuroQol-5 Dimensions, 3-level questionnaire
FIX-IT	Function Index for Trauma
FRI	Fracture-Related Infection
GO Tibia	Gentamicin versus No antibiotic for the treatment of Open Tibia fractures
GA	Gustilo Anderson
HIC	High-Income Country
IGOT	Institute for Global Orthopaedics and Traumatology
IRB	Institutional Review Board
LMIC	Low- and Middle-Income Country
MOI	Muhimbili Orthopaedic Institute
mRUST	Modified Radiographic Union Score for Tibia
MUHAS	Muhimbili University of Health and Allied Sciences
NIMR	National Institute for Medical Research
PMMA	Polymethylmethacrylate
RCT	Randomized Controlled Trial
REDCap	Research Electronic Data Capture
SAE	Serious adverse event
SAP	Statistical analysis plan
SSI	Surgical site infection
SC	Steering Committee
UCSF	University of California San Francisco

STUDY SUMMARY

Methodology	Masked, randomized controlled-trial
Coordinating Center	This study will be centrally coordinated by the Institute for Global Orthopaedics and Traumatology, University of California San Francisco (UCSF).
Clinical Site	Muhimbili Orthopaedic Institute (MOI), Dar es Salaam, Tanzania.
Background	The prevention of surgical site infections is important in patients with open fractures, as these wounds are often contaminated. Standard practice in the management of open fractures includes preoperative systemic antibiotics and surgical debridement. In addition to systemic antibiotics, local antibiotics applied directly to the surgical site have shown promise in reducing the rate of fracture-related infection (FRI). Gentamicin is a widely available, low cost antibiotic that holds promise for this application, but high-quality evidence supporting its use is lacking.
Objectives	The overall objective of this research program is to compare the effectiveness of intraoperative, locally administered gentamicin with no antibiotics for the management of open tibia fractures as measured by occurrence of fracture-related infection (FRI) (primary outcome) and occurrence of nonunion and unplanned fracture-related reoperations (secondary outcomes). The pilot trial specifically aims to assess feasibility of the definitive trial, including enrollment, retention, and data completeness.
Diagnosis and Main Inclusion Criteria	All patients 18 years of age or older who present to Muhimbili Orthopaedic Institute (MOI) for treatment of Gustilo-Anderson (GA) Type I, II or IIIA open tibia fractures will be screened for participation. Eligible patients must present to the hospital within 48 hours of their injury and receive surgical debridement of their open fracture wound within 7 days of their injury. The open wound must be primarily closable at the index debridement.
Treatment Groups	The pGO-Tibia trial will compare two solutions: 1) aqueous gentamicin solution (2mg/mL) in normal saline, or 2) normal saline only. A minimum of 5mL and a maximum of 40 mL of either solution will be injected into the fracture site immediately following primary closure of the traumatic wound.

Randomization	Allocation to the study groups will be performed using a web-based randomization. The randomization sequence was generated using randomly permuted blocks of 4, 6, and 8 with a 1:1 allocation ratio.
Study Outcomes	The definitive trial primary outcome is occurrence of FRI. Secondary outcomes of the definitive trial are the occurrence of 1) nonunion, and 2) unplanned fracture-related reoperation within 12 months of definitive fixation. Definitive trial subsidiary outcomes include health-related quality of life, radiographic healing, and clinical healing. A blinded adjudication process will judge each study event on occurrence of FRIs, nonunions, and unplanned fracture-related reoperations.
Feasibility Outcomes	This pilot trial will focus on the following feasibility endpoints: Recruitment: number of patients screened, number and proportion of patients screened that are eligible, enrolled, randomized, and receive intervention. Retention: number and proportion of randomized patients who attend each follow-up visit. Data collection completeness, solution quality control, masking and concealment, and evaluation of primary and secondary outcomes (reliability of fracture-related infection and mRUST scoring, radiographic image quality, and completeness of EQ-5D and FIX-IT).
Follow-Up	Study participants will be followed at 2 weeks, 6 weeks, 3 months, 6 months, 9 months, and 12 months from their fracture.
Sample Size	50 individuals per arm will be included in the feasibility trial.
Significance	FRIs place a significant burden on both the patient and the healthcare system, as they increase patient mortality, delay healing, decrease functional outcomes and health-related quality of life, and often require prolonged hospitalization or reoperation, increasing the cost of care. Given the consequences of open fracture complications, maximizing the effectiveness of prophylactic procedures is essential. The GO Tibia trial will provide necessary evidence to guide the use of local antibiotic application in prevention of FRIs in open fractures,

	and may significantly impact care and outcomes of open extremity fractures.
--	---

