2.0 STUDY AIMS AND HYPOTHESES

The study described herein is a single-center pilot trial to evaluate the feasibility of necessary protocols including, recruitment, retention, masking and concealment, intervention, and follow-up. The described pilot study will establish effect sizes for appropriate power calculations for a subsequent definitive trial.

The overarching objective of the definitive trial is to test whether injection of intraoperative local gentamicin impacts the rate of fracture-related infection following GA Type I, II or IIIA open tibia fractures in Tanzania. We hypothesize that the risk of fracture-related infection will be reduced by the intraoperative use of locally administered gentamicin at the time of wound closure.

2.1 Definitive Trial Specific Aims:

1. Compare the rate of fracture-related infection at one year after intraoperative local gentamicin injection or intraoperative local saline injection among adults treated operatively for GA Type I, II, or IIIA open tibia fractures. [Primary aim]
2. Compare the occurrence of 1) nonunion, and 2) unplanned fracture-related reoperation after intraoperative local gentamicin injection or intraoperative local saline injection among adults treated operatively for GA Type I, II, or IIIA open tibia fractures. [Secondary aims]
3. Evaluate the economic impact of fracture-related infection (FRI) after open tibia fractures in Sub-Saharan Africa including direct medical costs and lost productivity. [Secondary aims]

Null hypothesis: There is no difference in the rate of fracture-related infection between local gentamicin administration and saline administration for adult patients with GA Type I, II, or IIIA open tibia fractures treated in Sub-Saharan Africa.

Alternative hypothesis: Intraoperative local gentamicin administration decreases the occurrence of fracture-related infection in adult patients with GA Type I, II, or IIIA open tibia fractures treated in Sub-Saharan Africa.

2.2 Feasibility Trial Specific Aims:

Outcomes include rates of screening, enrollment, randomization, allocation, reliability of intervention, subject retention, and data completeness.

Specifically, feasibility outcomes are:

1. Recruitment: number of patients screened, number and proportion of patients screened that are eligible, enrolled, randomized, and receive intervention.

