radiographs will be obtained prior to hospital discharge and serum creatinine will be obtained pre-operatively and on postoperative day 2. If serum creatinine levels on postoperative day 2 are ≥ 1.5 times patient baseline and acute kidney injury is suspected, serum creatinine levels will be redrawn at two-week follow-up visit¹⁸. Personnel time and resources utilized will be directly observed using time and motion analysis, beginning from patient admission to the completion of surgery and transfer to the ward. The schedule of patient encounters and corresponding data to be collected is described in Table 2.

Participants will return to clinic for follow-up at 2 weeks, 6 weeks, 3 months, 6 months, 9 months, and 1 year following surgery.

Specifically, follow-up visits will include the following:

1. Two-week postoperative visit: The study investigator will review and record interval history since hospital discharge. The patient will complete a Visual Analog Scale for pain assessment. A physical examination will be performed to assess for signs of Fracture-related Infection. C-reactive protein level will be obtained. If serum creatinine levels on postoperative day 2 are ≥ 1.5 times patient baseline and acute kidney injury is suspected, serum creatinine levels will be redrawn.
2. Six-week postoperative visit: During the follow-up visit reminder telephone phone call, the study investigator will ask the five fracture-related infection (FRI) validation questions. At the visit, the study investigator will review and record interval history since the last appointment. The patient will complete a Visual Analog Scale for pain assessment. The study subject will complete a Work Productivity and Activity Impairment questionnaire (WPAI) to assess lost productivity, and patient reported outcome measure (EQ-5D). A physical examination will be performed to assess for signs of fracture-related infection (FRI). C-reactive protein level will be obtained.

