3. Three-month, six-month, nine-month, and 12-month postoperative visits: During the follow-up visit reminder telephone phone call, the study investigator will ask the five fracture-related infection (FRI) validation questions. At the visit, the study investigator will review and record interval history since the last appointment. The patient will complete a Visual Analog Scale for pain assessment. The study subject will complete a Work and Activity Impairment questionnaire (WPAI), the FIX-IT score for clinical healing, additional questions to address indirect costs and economic impact associated with their treatment, and patient reported outcome measure (EQ-5D). A physical examination will be performed to assess for signs of fracture-related infection (FRI). AP and lateral radiographs will be taken. C-reactive protein level will be obtained.

Table 2: Schedule of Events

Assessment	Hospital			Outpatient													
	Pre-Surgery		Surgery	Post-Surgery		2-weeks		6-weeks		3-months		6-months		9-months		12-months	
	Screening	Enrollment		≤ 48 hrs	Post Op												

Radiographs	•	•	•	•	•	•	•
Informed Consent	•						
Serum Creatinine*	•	•	•				
Randomization		•					
Intervention		•					
Baseline Data**			•				
Contact Information		•					
EQ-5D		•			•	•	•
Outcomes					•	•	•
Assessment***			•	•	•	•	•
FIX-IT					•	•	•
WPAI					•	•	•
C-reactive protein			•	•	•	•	•
Adverse Event					•	•	•
Screen			•	•	•	•	•

*** 2-week creatinine level will only be drawn if postoperative creatinine level is ≥ 1.5 times patient baseline and acute kidney injury is suspected

** demographic, medical history, injury characteristics

*** fracture-related infection, unplanned fracture-related reoperation

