4.7.2 Study Solution Administration

Following intraoperative randomization, the appropriate study solution is provided to the administering surgeon in a masked manner. The local solution injection is administered immediately following wound closure. As described previously by Lawing et al¹⁹, the solution is injected by inserting a 22-gauge needle down to bone through an anteromedial approach at the level of the fracture site such that the injected solution fills the wound cavity. A minimum of 5mL of study solution may be injected, and the injection is continued until either extravasation is seen through the traumatic wound or a maximum of 40mL has been administered, whichever occurs first.

For quality control, the efficacy of masked study solutions will be tested against standard organisms. This will occur once per month for the first 6 months and once every 3 months thereafter by the Muhimbili University of Health and Allied Sciences (MUHAS) microbiology lab, with results evaluated by unmasked study personnel.

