7.2 Consent

If a patient is deemed eligible for the study, designated study personnel will obtain informed consent from the patient (preferred) or proxy as soon as feasibly possible. The consent process will typically take place in the emergency room, prior to surgical fixation of their open fracture. To discuss their participation, a member of the study team will approach potentially eligible patients.

To obtain informed consent, study personnel should follow the below procedures:

- Present study information in a manner that is understandable to the potential participant.
- Discuss the study with the potential participant and answer any questions he or she asks.
- Allow the potential participant an opportunity to discuss participation with their family, friends, or family physician, if desired.
- Confirm that the participant understands the risks and benefits of participating in the study and that their participation is voluntary.
- Complete and obtain signatures for informed consent form and obtain contact information from the participant.

The process of obtaining and documenting informed consent forms will be completed in accordance with local Good Clinical Practice recommendations.

Upon providing informed consent, study participants will be followed for 12 months from their fracture. Given the short follow-up time, the need for a regular reassessment of consent will not apply; however, participants may withdraw their consent at any time.

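### In staged patients the reoperation window, counted from definitive fixation, opens after randomisation and closes after the last scheduled visit

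*Combined protocol and SAP*

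**What the plan says.** The Study Summary (Study Outcomes) times the secondary outcome as "unplanned fracture-related reoperation within 12 months of definitive fixation". The fuller definition in section 4.7.2 (Definitive Trial Outcomes) makes reoperation a binary variable and lists qualifying procedures, including debridement for infection and revision closure, but gives neither a window nor a starting date.

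Follow-up is counted in two ways. The Study Summary puts the last visits at "6 months, 9 months, and 12 months from their fracture", and section 7.2 agrees: "study participants will be followed for 12 months from their fracture". Section 4.4 instead has "6 months, 9 months, and 1 year following surgery". The Table 2 footnote on outcomes assessment covers "fracture-related infection, unplanned fracture-related reoperation", so reoperation is assessed at these scheduled visits.

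Randomisation belongs to the index operation. Section 4.3 places it in theatre once the wound is closed, and section 4.7.2 (Study Solution Administration) adds: "The local solution injection is administered immediately following wound closure". Section 4.6.3 shows that fixation at that operation comes before closure. Section 4.7.3 lets the surgeon choose temporizing or definitive stabilisation and keeps an external fixator on for at least 4-6 weeks and at most 3 months. Eligible patients must "receive surgical debridement of their open fracture wound within 7 days of their injury".

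**The concern.** The reoperation clock and the follow-up clock agree only if definitive fixation is done at the index operation. The plan explicitly allows otherwise. In a staged patient the clock starts at an event that follows randomisation, and both ends of the window are affected.

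- **Early end.** An unplanned debridement for infection after the injection but before definitive fixation falls outside the window, read literally. These are the reoperations closest in time to the intervention.
- **Late end.** The last part of the window lies after the final scheduled visit and is not observed.

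The outcome would then cover different periods in staged and unstaged patients, and adjudicators could apply different windows to the same event. The planned Fisher's exact test (section 5.2.2) takes no account of observation time, so it would not correct for this.

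**Working it through.** The plan gives no figure for this point. Its sample size (356 per group, 712 in total, 712/0.80 = 890 with 20% loss) is based on infection rates of 12% and 6%. It reproduces exactly and does not depend on the reoperation window. The check is therefore date arithmetic.

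**Inputs**

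- S, days from fracture to index operation: 0 to 7 (Study Summary, inclusion criteria).
- D, days from index operation to definitive fixation: not stated. D = 0 if index fixation is definitive, including external fixation used as definitive treatment. For staged patients I assume the fixator durations in section 4.7.3: 4 weeks = 28 days, 6 weeks = 42 days, 3 months taken as 13 weeks = 91 days.
- Window length: 12 months, taken as 365 days.

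**Formulas, in days from fracture**

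- Randomisation and injection: S.
- Reoperation window: from S + D to S + D + 365.
- Last visit: S + 365 if timed from surgery, 365 if timed from fracture.
- Early gap (randomisation to window opening): (S + D) - S = D.
- Late gap (last visit to window end): (S + D + 365) - (S + 365) = D with visits from surgery; (S + D + 365) - 365 = S + D with visits from fracture.

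**Results** (percentages are of 365 days)

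| Assumed D | Early gap | Late gap, visits from surgery | Late gap, visits from fracture, S = 7 |
|---|---|---|---|
| 0 | 0 | 0 | 7 (1.9%) |
| 28 | 28 | 28 (7.7%) | 35 (9.6%) |
| 42 | 42 | 42 (11.5%) | 49 (13.4%) |
| 91 | 91 | 91 (24.9%) | 98 (26.8%) |

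Any D above zero produces both gaps. The difference between the two visit origins never contributes more than 7 days, so the conflict that matters is with definitive fixation.

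**The case against.** The strongest reply is that little is lost in practice. Section 4.7.2 says that infections seldom first appear beyond a year after surgery, and with visits timed from surgery the late gap lies entirely beyond that year. This stands: few new infections are expected there. What remains is late reoperation for union or for earlier infection, for which no rate is given.

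A second reply is that the phrase could loosely include reoperations before definitive fixation. That reading closes the early gap but not the late one, and the text does not say which is meant.

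Third, the window appears only in the Study Summary, for a secondary outcome of a later trial, and section 5.2 says the methods are given mainly for planning and will be revised. That limits the importance. But the outcome section states no competing window, so nothing replaces the summary wording.

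A reader might infer four stronger claims that the documents do not support:

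- *The comparison is biased.* Whether index fixation is temporizing or definitive is settled before randomisation, and nothing shows that coverage of the window differs by arm.
- *Up to a quarter of reoperations are missed.* The percentages are shares of time under an assumed delay, in a subset of unknown size. They are not shares of events.
- *The infection endpoint has the same fault.* The primary aim in section 2.1 ("Compare the rate of fracture-related infection at one year after intraoperative local gentamicin injection") matches the surgery-based visits, and injection and surgery fall on one date. Only the 7-day fracture-origin difference remains. Section 5.2.1 gives no start for observation time, but that is missing detail in the infection analysis, as is the time origin for the combined analysis.
- *The fixation subgroup contradicts itself.* The short label in the section 4.7.2 list can be read as an abbreviation of the definitive-fixation wording that introduces it. Which fixation to use is partly a choice of question, and section 5.2.2 already treats conclusions from subgroups and adjustments as hypothesis-generating.

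**Conclusion.** The conflict is real and should be corrected before the definitive trial. For staged patients the stated window starts after randomisation and ends after scheduled observation. That follows from the plan's own definitions and needs no assumption beyond some patients having definitive fixation later than the index operation.

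The size is unknown. If the fixator duration is taken as the delay, the shift is 28 to 91 days with visits from surgery, and the late gap reaches at most 98 days with visits from fracture. For patients fixed definitively at the index operation it is 0 to 7 days. The more consequential part is the early gap, because it drops events near the injection. The late gap is expected to hold few new infections.

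No between-arm bias is shown. The pilot's descriptive feasibility results are little affected; the point concerns a planned secondary outcome of the definitive trial.

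**What to change.** In the Study Summary and in section 4.7.2 (Definitive Trial Outcomes), define the outcome as any unplanned fracture-related reoperation from randomisation at the index operation through 12 months. A planned second-stage fixation stays outside the outcome, which covers unplanned procedures only. In the Study Summary, section 4.4 and section 7.2, time all visits from surgery/randomisation, so that the 12-month visit closes the window. The nonunion criterion tied to the 12-month visit needs no change.

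This makes the window uniform, observable and anchored at randomisation. It does not recover later events: in staged patients, reoperations more than 12 months after the index operation would not count.

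A minor addition concerns fixation as a covariate. Where section 5.2.2 lists method of fixation at baseline, use the fixation in place at the end of the index operation, because later definitive fixation is post-randomisation. If the section 4.7.2 subgroup stays defined by definitive fixation, report it as a post-randomisation subgroup for staged patients.

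The cost is a wording change, with no added visits and no change in sample size. It may need approval from both ethics boards (sections 7.1 and 7.4). Someone should also confirm that the case report form records index fixation, since the listed baseline data do not name it.

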1.0 INTRODUCTION

1.1 Open Tibia Fractures

Open tibia fractures often result from high-energy trauma¹. These fractures represent an orthopaedic emergency associated with high morbidity and mortality. Fracture management includes systemic antibiotic prophylaxis, tetanus booster, wound irrigation and surgical debridement, and fracture stabilization^{2,3}. Open fractures are contaminated¹, and even with prompt treatment, infection can occur in up to 40% of cases^{3,4,5}. SSIs place a significant burden on both the patient and the healthcare system, as they increase patient mortality, delay healing, decrease functional outcomes and health-related quality of life, and often require prolonged hospitalization or reoperation, increasing the cost of care^{6,4,7}.

1.2 Prevention of Infection

Because surgical site infections have such profound consequences, prevention is crucial. Intravenous antibiotics are essential in reducing the risk of infection, but their dosage is limited by systemic toxicity, and local concentrations are diminished by the compromised blood supply at the site of injury⁵. Local antibiotics administered intraoperatively directly in the traumatic wound offer an additional method of infection prevention⁸⁻¹⁰. A recent meta-analysis found decreased incidence of infection in both spine and trauma surgeries, but this effect was absent with more rigorous study designs¹¹. This study demonstrated that vancomycin significantly reduces gram-positive infections without appearing to affect the incidence of gram-negative infections, which are the second most common pathogen in SSIs after open fracture¹¹. In addition, the relatively high cost of vancomycin may prohibit widespread use, particularly in low-income countries.

